### 10.4.2 EVALUATION OF SUCCESS OF BLINDING

Blinding will be evaluated using the Adverse Events Questionnaire which will be administered after each stimulation session. On day 5 of stimulation and at the final study session, we will also ask the participant whether they believe they have received stimulation.

### 10.4.3 BREAKING THE STUDY BLIND/PARTICIPANT CODE

This is a double blind clinical trial. The participant and researchers will remain blinded to stimulation conditions through the completion of data collection. In the event of an AE/SAE, the PI will be able to determine the stimulation condition of the participant.

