*Risk of Injury and Discomfort:* Transcranial current stimulation has been used without any reports of serious side-effects for more than a decade. This stimulation mode has NOTHING to do with electroconvulsive therapy that applies many orders of magnitude higher stimulation current. Rather, transcranial current stimulation is so weak that it does not cause super-threshold activation of neurons ([name] and McCormick, 2010). In particular, tACS has been used without reports of any serious side-effects. Some participants report a transient mild tingling, burning, or itching underneath the electrodes and headache, but no other side effects have been noted. Importantly, it remains unclear if these mild side-effects were caused by the transcranial brain stimulation. In order to monitor these side-effects, we will be administering an adverse effects stimulation questionnaire (*Attachments 1 & 2*) after each stimulation session to document whether these effects were experienced. Research personnel present during these sessions will also check in with the participant periodically during the stimulation to see whether they are comfortable. If any side-effect occurs (rated by the participant as stronger than "moderate") or the participant is experiencing severe discomfort, the stimulation will be immediately stopped.

While not previously reported with tDCS or tACS in humans, there is a theoretical possibility that stimulation of neuronal circuits could lead to epileptic discharges. To minimize this occurrence, we screen and exclude patients with personal and family history of neurological conditions from the study. If abnormalities or a seizure is witnessed during the course of the study, the subject will be referred to a neurology clinic for further evaluation and treatment.

We have no evidence that our treatment paradigms will increase auditory hallucinations if not treated (receive the sham treatment), as participants, will be by definition, stable. If an enrolled patient shows signs of increase symptoms that were not apparent during enrollment, a referral to UNC Psychiatry will be made. [name], Co-I, will facilitate this process.

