#### 8.1.1 DEFINITION OF ADVERSE EVENTS (AE)

**Adverse Event:** An AE, as defined by the NIH, is any unfavorable changes in health, including /abnormal laboratory findings that occur in trial participants during the clinical trial or within a specified period following the trial.

All AEs including local and systemic reactions not meeting the criteria for “serious adverse events” will be captured on the appropriate CRF. In addition, the AE Interview will be completed by the study coordinator during each lab visit (see attachment). For any Adverse events reported, a clinician will evaluate and indicate the severity of the event(s). The AE report form (*Appendix A*) will be completed for any reported AE. The AE form includes the following: what is known about the therapy and previous reported side effects, if the AE occurred in temporal relation to the therapy, whether or not the AE improves or disappears when treatment is stopped, whether the AE is a worsening of baseline symptoms or related to a concurrent medical condition or medication use. Once complete, both of these forms will be given to the PI and the Co-I who will review, comment and sign the forms. Completed forms will be placed in the participant’s folder.

The study coordinator will document any AE occurrence on the AE log (*Appendix B*) which includes information such as the date of the AE, severity, relationship to the treatment (assessed by the PI), actions taken, and outcome(s). The log will be reviewed and initialed by the PI 72 hours after being completed. All AEs occurring during the clinical trial will be documented appropriately regardless of relationship to tACS. All AEs will be followed to adequate resolution and will be graded for severity and relationship to the study treatment. Any medical condition noted at the initial session will be considered as baseline and not reported as an AE.

All AEs will be graded for severity using the following guidelines.

- **Asymptomatic:** the participant is exhibiting no symptoms due to the event; no treatment needed.
- **Mild** Adverse Event– Event results in mild or transient discomfort, not requiring intervention or treatment; does not limit or interfere with daily activities (e.g., insomnia, mild headache).

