### 8.2.2 RELATIONSHIP TO STUDY AGENT

The PI and Co-I will together determine whether an AE is associated with the study treatment. The event will be labeled associated if the event is temporally related to the administration of the therapy and no other factors can explain the event. The event will be labeled as not associated if the event is temporally independent of the study treatment and can be explained by external factors such as major life events.

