#### 8.6 SAFETY OVERSIGHT

Safety oversight will be under the direction of a DSMB composed of [name], an epidemiologist, a biostatistician and one or more clinical researchers. The DSMB will review AEs every 6 months whereas the medical monitor will review AEs in real time and make decisions as to each participant's continuation in the trial.

The PI will review AEs weekly with research team and may request additional review by Co-I on a case-by-case basis. The medical monitor will also be present at weekly meetings in order to discuss/explain any event(s) that may occur.

Every 6 months DSMB will review blinded AE reports. If there is reason to view unblinded information, the DSMB will directly receive the list of participants' identification numbers from a [name] Lab member, not otherwise associated with this clinical trial. Participant identification number will be displayed in a table according to the four treatment-sequence groups of the study; however the specific treatment regimens of the four groups will not be disclosed. This will allow the DSMB to compare the four treatment groups.

Reasons for stopping the study and asking for further investigation include; decrease in cognitive abilities based on baseline and end of study data (>25% decrease in scores in 2/10 of the first participants or 20% of participants overall.). In addition, as mentioned above, if a seizure occurs during a study visit, the clinical trial will be temporarily be placed on hold for further investigation.

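### Section 10.4.3 lets the PI learn a participant's allocation after any adverse event, with no threshold of seriousness or need, although the PI also judges relatedness

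*Combined protocol and SAP*

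**What the plan says.** Section 10.4.3 of the protocol makes two statements in succession. The first is a general promise: "The participant and researchers will remain blinded to stimulation conditions through the completion of data collection". The second gives the PI access: "In the event of an AE/SAE, the PI will be able to determine the stimulation condition of the participant". The section does not say how serious the event must be, whether the allocation must be needed for the participant's care, who releases the code, whether the release is recorded, or who else may be told.

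The trigger takes its breadth from the definitions in Section 8. Section 8.1.1 defines an adverse event as "any unfavorable changes in health, including /abnormal laboratory findings that occur in trial participants during the clinical trial". The grading there, repeated in Section 8.2.1, starts at asymptomatic. The mild grade is for an event that "does not limit or interfere with daily activities (e.g., insomnia, mild headache"). Section 2.3.1 lists effects already seen with this type of stimulation: "Some participants report a transient mild tingling, burning, or itching underneath the electrodes and headache".

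The PI has two further tasks that bear on this.

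- **Relatedness.** Section 8.2.2: "The PI and Co-I will together determine whether an AE is associated with the study treatment". The adverse event log described in Section 8.1.1 likewise records "relationship to the treatment (assessed by the PI").
- **Weekly review.** Section 8.6: "The PI will review AEs weekly with research team". Section 13.1 gives questionnaire administration to the study coordinator and research assistants.

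**The concern.** Two things are at stake.

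The first is safety attribution. Section 8.2.2 asks whether an event is temporally related to treatment and whether anything else explains it. The second question calls for judgement, and knowing that a participant had sham or active stimulation can tilt the answer. The expected direction is that events under active stimulation are called related more readily than the same events under sham. Nothing requires the judgement to be recorded before the code is opened.

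The second is the primary outcome. Section 7.1 describes the AHRS as a structured interview, so it depends on what the interviewer knows and expects. The PI discusses adverse events each week with the team responsible for administering the assessments. If the PI has learned an allocation, that meeting is a route by which it could reach a rater. Section 2.2 reports a strong placebo effect in the group's earlier pilot, which is a reason to guard expectation closely in this trial.

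**Working it through.** The plan gives no figure to reproduce. The check sets the sections side by side and then works out the scale under stated assumptions.

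**1. Is there a threshold anywhere?**

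| Question | Source | Answer |
|---|---|---|
| What opens the code to the PI? | 10.4.3 | Any AE or SAE |
| Lowest grade that counts as an AE | 8.1.1, 8.2.1 | Asymptomatic, then mild |
| Must the event be related to stimulation to be documented? | 8.1.1 | No |
| Is access limited to serious or emergency cases? | No section | Not stated |
| Is a log of code-breaks required? | No section | Not stated |

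The permission therefore covers minor events.

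**2. Do the documents show a need for it?** Section 8.6 gives real-time review and the decision on continuation to the medical monitor. If the DSMB asks for unblinded information, it receives participants sorted into four groups without being told which regimen each group has. The PI thus has fuller access than the DSMB, on a lower trigger, and no reason is given.

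**3. Who holds the code?** Section 10.4.1 leaves the master list solely with a lab member who has no other study duty. The PI would presumably have to ask that person, but no condition for release is written down.

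**4. How many participants could be affected?**

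- Sessions per participant: 5 daily + 8 weekly = 13 (Protocol Summary; Sections 7.4.3 to 7.4.6).
- Participants: 40.
- Chance *p* of a recorded adverse event per session: not given, so assumed, with sessions treated as independent.
- Chance of at least one event = 1 − (1 − p)^13.

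| Assumed p | At least one event | Expected of 40 |
|---|---|---|
| 1% | 1 − 0.99^13 = 12% | 4.9 |
| 2% | 1 − 0.98^13 = 23% | 9.2 |
| 5% | 1 − 0.95^13 = 49% | 19.5 |
| 10% | 1 − 0.90^13 = 75% | 29.8 |

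For the same average rate, clustering of events in the same people would lower these shares. Events arising outside sessions, which Section 8.1.1 also counts, would raise them. The table shows who could meet the trigger, not whose code would be opened.

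**The case against.** The section is headed as dealing with breaking the blind, so its two sentences can be read as a rule and its exception. The exception is permissive, concerns one participant at a time and names one person. That reading is fair, and it removes the charge of a flat contradiction. It does not supply the missing condition: an exception triggered by any adverse event is too wide to protect the rule.

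A reader might infer that the clause undoes the blind of the trial. The documents do not support that. Nothing in 10.4.3 unblinds participants or raters. Section 9 gives the PI read-only access to the database, no section makes the PI an AHRS rater, and no section says that allocation is disclosed at the weekly meetings. That the coordinator and assistants conduct the AHRS interview is itself inferred from Section 13.1. A reader might also suppose that an unblinded PI decides who continues; Section 8.6 gives that decision to the medical monitor.

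Two further objections stand in part. Section 8.1 links adverse event reporting of session discomfort to discomfort above moderate, while Section 8.1.1 calls for a form for any reported event, so whether ordinary tingling is a trigger is unsettled. Also, relatedness is judged jointly with the Co-I, to whom 10.4.3 gives no access; Section 10.2 plans no analysis of relatedness; and the DSMB routinely reviews blinded reports. These points limit the consequences. They do not ensure that the relatedness judgement is made blind.

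**Conclusion.** The point holds as a defect in the code-break rule. Section 10.4.3 permits the PI's own blind to be opened for adverse events of any grade, with no test of need and no record, and the PI also takes part in judging relatedness. The direct consequence is that relatedness may be assessed with the allocation known. The indirect one, leakage to AHRS raters through the weekly review, is a risk that the text does not close.

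The size cannot be fixed from the documents. Under an assumed 1% to 10% chance of an event per session, independent over 13 sessions, about 12% to 75% of participants would have at least one event. The range is too wide to count as evidence of how often codes would be opened, and the conclusion does not depend on it. It rests on the wording of 10.4.3, 8.1.1, 8.2.2 and 8.6. It does not show that the AHRS comparison is biased.

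**What to change.** Rewrite Section 10.4.3 so that its two sentences agree:

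- Allow a code-break only where a documented safety need for that participant's care requires the allocation.
- Have the holder of the master list release that participant's code alone.
- Require the PI and the Co-I/medical monitor to record relatedness before any release.
- Bar disclosure to anyone who rates or administers outcomes, including at the weekly meetings.
- Log every code-break and report it with the results.

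Simply moving access from the PI to the medical monitor would not be enough. Sections 8.3, 8.4.1 and 11 write the medical monitor and Co-I as one role, the Co-I shares the relatedness judgement under Section 8.2.2, and Section 8.6 has the monitor at the same weekly meetings. Recording relatedness first and barring disclosure are therefore needed whoever receives the code.

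The cost is a wording change and a short log. The small downside is that the PI loses access to allocation for minor events.

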## 11 SOURCE DOCUMENTS AND ACCESS TO SOURCE DATA/DOCUMENTS

**Human Research Committee (IRB):**

- All IRB Correspondences are on file.
- The study staff is IRB approved prior to performing any study procedures.
- Adverse events and deviations are reported to IRB per current guidelines.
- All versions of the IRB protocols and informed consent forms are on file.

**Informed Consent:**

- Initial consent documented in REDCap via eConsent form.
- Ensure that participant identification is on all pages of the physical copy of the ICF.
- There is documentation that the participant is given a copy of the consent form.
- The participant and study representative signed and dated the consent form for him/herself.
- The participant initialed and dated all appropriate pages on the informed consent form.
- Note to file (*Appendix G*) made for any informed consent deviations.
- Ensure a valid (current version date) copy of the consent form was used.

**Protocol:**

- Confirm that the study staff is conducting the study in compliance with the protocol approved by IRB
- The protocol deviations (exceptions and violations) are documented in the participant chart and reported to IRB as required.

**Source Documents:**

- Each participant binder will contain a checklist to ensure that each binder has each source document. The checklist will be dated by the researcher for each time an assessment is administered.
- Review participant charts to ensure the accuracy, completeness and legibility of the data
- Any correction made to the source documents is dated, initialed, and explained. The original entry should not be obscured.
- The protocol specific source documents are on file.
- Source documents are completed in ink.
- Note to files (*Appendix G*) are made for missing or incomplete data and to explain any discrepancies or additional comments.

**Electronic Case Report Forms (eCRF)**

- Ensure the data reported on the eCRF is consistent with the source documents.
- Discrepancies between the source documents and eCRF are explained in a note to file (*Appendix G*) or captured in a comment in the eCRF.

**DNA**

- Participant names will not be on any of the samples collected at the initial session. DNA testing is performed within the University of North Carolina at Chapel Hill and the samples are not shared with or processed by any third party outside the university.

The research coordinator, research assistants, and PI will have access to all of the above information. Co-I/medical monitor will have access to files upon request as they will need access to the locked rooms and filing cabinets in which these documents are located. The key linking dummy identifiers with subject information will be securely destroyed after completion of data acquisition.

## **12      ETHICS/PROTECTION OF HUMAN SUBJECTS**

### **12.1    ETHICAL STANDARD**

The investigator will ensure that this study is conducted in full conformity with the principles set forth in The Belmont Report: Ethical Principles and Guidelines for the Protection of Human Subjects of Research, as drafted by the US National Commission for the Protection of Human Subjects of Biomedical and Behavioral Research (April 18, 1979) and codified in 45 CFR Part 46 and/or the ICH E6; 62 Federal Regulations 25691 (1997).

### **12.2    INSTITUTIONAL REVIEW BOARD**

The Office of Human Research Ethics is responsible for ethical and regulatory oversight of research at UNC-Chapel Hill that involves human participants. The OHRE administers, supports, and guides the work of the Institutional Review Boards and all related activities. Any research involving human participants proposed by faculty, staff, or students must be reviewed and approved by an IRB before research may begin, and before related grants may be funded. OHRE and the IRBs are critical components of the coordinated Human Research Protection Program, which serves to protect the rights and welfare of human participants. All components of this program must work together to ensure institutional compliance with ethical principles and regulatory requirements. The following is a mission statement for the coordinated Human Research Protection Program:

The University of North Carolina at Chapel Hill is committed to expanding and disseminating knowledge for the benefit of the people of North Carolina and the world. An important part of that commitment to knowledge is research of the highest quality on all aspects of the health and behavior of people, and such research is only possible through the participation of humans as research participants. Human participants are partners in research and a precious resource to the university. At UNC-Chapel Hill, human participant research is a privilege, but not a right. Consistent with that philosophy, it is the mission of the UNC-Chapel Hill Human Research Protection Program to ensure that

1. The rights and welfare of human participants are paramount in the research process;
2. The highest standards of ethical conduct are employed in all research involving human participants;
3. Research investigators are properly trained in the ethical and regulatory aspects of research with human participants;
4. Research investigators deal honestly and fairly with human participants, informing them fully of procedures to be followed, and the risks and benefits of participating in research; and

Research using human participants at UNC-Chapel Hill conforms to all applicable local, state, and federal laws and regulations and the policies of the university.

### **12.3    INFORMED CONSENT PROCESS**

---

### 12.3.1 CONSENT/ASSENT AND OTHER INFORMATIONAL DOCUMENTS PROVIDED TO PARTICIPANTS

Informed consent is a process that is initiated prior to the individual's agreeing to participate in the study and continues throughout the individual's study participation. Extensive discussion of risks and possible benefits of tACS will be provided to the participants and their families. eConsent documentation via REDCap is required prior to the administration of any assessments used in this study. A physically signed consent form describing, in detail, the study intervention, device, procedures, and risks will be provided to the participant. Written documentation of informed consent is required prior to the administration of any treatment used in this study. All consent forms will be IRB-approved and updated with any new information as modifications are made throughout the study.

---

### 12.3.2 CONSENT PROCEDURES AND DOCUMENTATION

Together, the researcher and potential participants will review the clinical trial in its entirety. At several intervals during the consent review, the researcher will ask the participant questions that will assess the comprehension of the information in the consent. If the participant is unsure or does not know, the researcher will return to that section and more carefully explain the information. Participants must complete the eConsent form via REDCap before any verbal assessments take place. Participants must sign the physical informed consent document prior to any additional study procedures taking place. If needed, the participants will have the opportunity to discuss the study with their surrogates or think about it prior to agreeing to participate. Participants may withdraw consent at any time throughout the course of the trial. A copy of the signed informed consent document will be given to the participants for their records. The rights and welfare of the participants will be protected by emphasizing to them that the quality of their medical care will not be adversely affected if they decline to participate in this study.

---

### 12.3.3 EXCLUSION OF SPECIAL POPULATIONS

Non-English speaking individuals are excluded because the ability to accurately and completely communicate study information, answer questions about the study, and obtain consent is necessary. Female participants will be asked if there is any reason to believe they might be pregnant. Pregnant participants will be excluded despite the fact that theoretical risk to mother or fetus is exceedingly small, since no safety data for pregnancy is known to exist for transcranial current stimulation studies. All women of child-bearing potential will be asked to take a pregnancy test during the 1st day of stimulation in order to determine eligibility for the study.

---

